4. SELECTION OF STUDY POPULATION

4.1 Number of Subjects Required

An estimated number of 15 patients at least 18 years of age will be enrolled in this study to ensure 10 analyzable patients who complete the study. Dropouts secondary to poor compliance or patients who have more than two weeks of radiation treatment break will be excluded and will be replaced by enrolling more patients.

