1 INTRODUCTION

1.1 Oral Mucositis

Oral mucositis is an acute injury to the mucosal lining of the head and neck region associated with radiotherapy and chemotherapy. The inflammatory response to injury can cause pain and discomfort that result in dysphagia and odynophagia, excessive secretions and associated nausea. Patients often require a temporary feeding tube to go through radiotherapy. The severity of radiation-induced mucositis is associated with the volume of mucosa irradiated, radiation dose and fractionation, concomitant use of chemotherapy, and patient factors such as tobacco and alcohol use, genetic predisposition and comorbidities. It has a negative impact on patients' quality of life and compliance with treatment that often result in unintended radiation treatment breaks. It can also cause weight loss making radiation dose delivery less optimal secondary to significant tissue volume changes. These can unfavorably affect radiotherapy local control rates.

Currently there have been no agents that are clinically proven to prevent radiation-induced mucositis. The management strategies for oral mucositis are mainly supportive care including adequate pain control, use of protective coating agents or devices, feeding tube use to bypass the irradiated oral mucosa for nutrition and hydration, and other symptomatic management strategies.

Topical and systematic administration of analgesics is the most commonly used first-line therapy. There are many oral agents (various mouth rinses or coating devices) for the management of mucositis symptoms, but none have shown convincing benefits in treating radiation-induced mucositis. The FDA has approved several products not as active pharmacologics but as devices to relieve mucositis symptoms. Among those approved are Gelclair, MuGard, Mucatrol, and Caphasol. Other approaches, such as growth factor GM-CSF, Amifostine, antiseptic and antimicrobial agents, and anti-inflammatory agents have been tested but are mostly negative in trials¹.

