3. STUDY PLAN

3.1 Overall Study Design

This trial will be a single-center, open-label, proof of concept trial to evaluate the efficacy, safety and tolerability of SAN005 treatment regimen when administered to adults at least 18 years of age for the prevention and treatment of oral mucositis.

Subjects will enter the Screening Period once the informed consent process has been completed. Subjects who are scheduled to receive radiation with or without concurrent chemotherapy and meet all of the inclusion criteria and none of the exclusion criteria will be eligible for the study:

Once subject eligibility is confirmed the subject will start SAN005 treatment on Day 1 of their radiation treatment. All subjects will receive active medication in the study with the first dose administered on Day 1.

Subjects will be instructed on the administration of study medication thrice daily till oral mucositis resolves. Subjects will return to the clinic once a week while receiving radiation and then once every two weeks once their radiation has been completed and then until their mucositis has resolved for the Final Study Visit.

Preliminary Efficacy Evaluation will be the severity of pain rated by the NRPS and mucositis grade by RTOG criteria at Visit 7 (Day 36). Additional secondary efficacy evaluations will include the severity of pain rated by the NRPS and mucositis grade by RTOG criteria at each study visit, frequency of the PEG tube for feeding during the duration of treatment and weight loss from baseline through Visit 5 and 7. The time of mucositis onset and duration will also be used in assessing efficacy. Additional secondary and exploratory endpoints will be outlined in the statistical analysis plan. The overall efficacy is determined by comparing the data to historical controls.

Safety will be assessed by evaluating adverse events (AEs) with respect to severity, duration, and relationship to study drug. In addition tolerability evaluations will be performed at each study visit.

During the active treatment period, subjects will return to the study site according to the study schedule for interim assessments, review of subject dosing diaries, and assessment of concomitant medication and adverse events (AEs).

The study design is summarized in Figure 3-1.

Figure 3-1 **Study Design**

Pretreatment	Treatment		Follow-up
Day 0	Day 1 Baseline	Day 8,15,22,29,36,43 (\pm 2 day, weekly)	Every other week until mucositis resolves or it reaches Visit 10

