6.6 Subject Replacement

Subjects who prematurely discontinue the study will not be replaced. Up to 15 subjects will be enrolled to ensure 10 subjects complete the trial.

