7.6.1 Pain Assessment

At each Study Visit the NRPS will be recorded for mouth pain and pain upon swallowing. For the primary efficacy assessment the NRPS scale at baseline will be compared to Week 5. Subjects that complete at least 80% of treatments as determined by the diary and confirmed by the weight of the returned study product will be included in the efficacy analysis.

If possible, the same investigator who completes the scoring at Baseline should complete all subsequent assessments for the patient.

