8. STATISTICAL METHODS AND DETERMINATION OF SAMPLE SIZE

8.1 General Considerations for Data Analysis

All statistical processing will be performed using the SAS® system (Version 9.12 or higher). Up to 15 subjects will be enrolled in this study to ensure a minimum of 10 subjects complete the study. The primary efficacy analysis of the study will be the determination of the NPRS from baseline to Visit 7 (Day 36).

Secondary efficacy endpoints will be evaluated using descriptive statistics. No interim or subgroup analyses are planned.

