8.4.2 Full Analysis Set

The Full Analysis Set (FAS) is defined as all subjects who receive at least one administration of the investigative study regimen and who had at least one post-Baseline efficacy assessment. The FAS population will be the primary population used for efficacy analysis.

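### Section 4.1 excludes and replaces compliance dropouts and patients with long radiation breaks, Sections 6.6 and 8.1 bar or cap replacement, and no analysis set says what exclusion for a break means

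*Combined protocol and SAP*

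**What the plan says.** **Replacement and numbers.** Section 4.1 estimates 15 patients to obtain 10 analyzable ones. It then says that dropouts for poor compliance and "patients who have more than two weeks of radiation treatment break will be excluded and will be replaced by enrolling more patients". It gives no upper limit. Section 6.6 says "Subjects who prematurely discontinue the study will not be replaced" and limits enrolment to 15. Section 8.1 repeats the limit: "Up to 15 subjects will be enrolled in this study to ensure a minimum of 10 subjects complete the study".

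**Analysis sets.** The ITT, FAS, PP and safety definitions in Sections 8.4.1 to 8.4.4 do not mention radiation breaks or refer to Section 4.1. Compliance is partly covered: Section 8.4.3 counts under 80% compliance as a major violation for the PP set, and Section 7.6.1 admits to the efficacy analysis "Subjects that complete at least 80% of treatments as determined by the diary" and confirmed by the weight of returned product.

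**Primary efficacy set.** Section 8.4.2 says "The FAS population will be the primary population used for efficacy analysis", and Section 8.4.3 calls the PP set secondary. Section 8.5.4 names the PP set as primary.

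**Outcome and comparison.** Section 3.2 assesses primary efficacy by pain score (NRPS) and RTOG grade at Visit 7 (Day 36). For pain, Section 7.6.1 says "For the primary efficacy assessment the NRPS scale at baseline will be compared to Week 5". Section 3.1 adds: "The overall efficacy is determined by comparing the data to historical controls".

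**Link between mucositis and breaks.** Section 1.1 says that mucositis harms "compliance with treatment that often result in unintended radiation treatment breaks".

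**The concern.** Two things are unsettled: whom to enrol and whom to analyse. A site following Section 4.1 would replace a compliance dropout; a site following Section 6.6 would not. An analyst who meets a patient with a three-week break cannot tell whether that patient is merely not counted toward the 10, or is taken out of the efficacy result.

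The second reading matters for inference. A radiation break happens after baseline, and the protocol itself describes breaks as a consequence of mucositis, the condition being measured. Dropping patients for such a break can therefore select on the outcome. The trial has one arm and efficacy is judged against historical controls, so no concurrent arm is subject to the same exclusion. With 10 to 15 patients, one or two removals visibly move any proportion.

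**Working it through.** **1. Where the rules collide.**

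| Patient | Section 4.1 | Sections 6.6 and 8.1 | Result |
|---|---|---|---|
| Drops out for poor compliance | Exclude and replace | Premature discontinuation: no replacement | Direct contradiction |
| Break over two weeks, stays on study | Exclude and replace | Not a discontinuation, but at most 15 enrolled | Conflict only if replacement would pass 15 |

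The first row rests on Sections 6.3, 6.4 and 7.5, all of which allow withdrawal for noncompliance.

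**2. The plan's own figure.** The documents give no dropout rate, so 15 cannot be derived independently. Working back, 15 enrolled and 10 remaining tolerate a loss of 1 - 10/15 = 33.3%, and 10/(1 - 1/3) = 15. This is circular: it shows that the two numbers fit each other, not that one third is the expected loss.

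**3. One dataset, several rules (all counts assumed).** Take 15 treated patients, all with Visit 7 data. Six have RTOG grade 3-4, a cut-off chosen here because the protocol defines none. Three are under 80% compliant, one of them severe. Two others have breaks over two weeks. Intervals are exact 95%.

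| Rule | Severe / analysed | Share | Interval |
|---|---|---|---|
| FAS | 6/15 | 40% | 16 to 68% |
| PP as written (remove the 3 noncompliant) | (6-1)/(15-3) = 5/12 | 42% | 15 to 72% |
| 4.1 as removal, both break patients severe | (5-2)/(12-2) = 3/10 | 30% | 7 to 65% |
| 4.1 as removal, neither break patient severe | 5/(12-2) = 5/10 | 50% | 19 to 81% |

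**4. Expected effect of selective exclusion.** Let r be the true severe share, and s and n the exclusion probabilities for severe and non-severe patients. The expected observed share is r(1-s) / [r(1-s) + (1-r)(1-n)]. With r = 0.40 (assumed):

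- s = 0.50, n = 0: 0.20/0.80 = 25.0%
- s = 0.40, n = 0.10: 0.24/0.78 = 30.8%
- s = 0.20, n = 0.05: 0.32/0.89 = 36.0%
- s = n: 40.0%, no bias
- s = 0.05, n = 0.20: 0.38/0.86 = 44.2%

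For mean NRPS change, removing a fraction f shifts the mean by -f × (mean change of removed - mean change of kept). If 2 of 15 are removed and their change is 2 points worse, the shift is -(2/15) × 2 = -0.27; if 2 points better, +0.27.

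**5. A force in the other direction.** Section 7.3 says radiotherapy is not given at weekends. Assuming five weekday sessions a week, Days 1 to 35 hold 25 sessions and any 14 consecutive days hold 10. A break over two weeks that ends before Day 36 leaves at most 25 - 10 = 15 sessions, or 15/25 = 60%. Keeping such patients can lower Visit 7 scores without any drug effect. A break that starts after Day 36 cannot change the Visit 7 value.

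**6. Completers if 15 are enrolled without replacement.** Binomial probability of at least 10 completers, by assumed completion rate:

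| Completion rate | At least 10 | Fewer than 10 |
|---|---|---|
| 60% | 40% | 60% |
| 66.7% | 62% | 38% |
| 70% | 72% | 28% |
| 75% | 85% | 15% |
| 80% | 94% | 6% |

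**The case against.** **Small, unpowered study.** Section 8.2 disclaims statistical sizing, and this is a proof-of-concept trial of about 15 patients. That is true and it limits the stakes, but it does not resolve contradictory enrolment instructions or two different primary sets.

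**Compliance is already handled.** This largely stands. A reader might infer that no analysis set covers either kind of exclusion. The documents do not support that: Sections 8.4.3 and 7.6.1 deal with under 80% compliance, although neither refers to Section 4.1. The complete gap concerns radiation breaks. The PP violation list is open-ended, so breaks could be added later, but deciding that once open-label data are in hand is what prespecification should prevent.

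**The bias is speculative.** Also largely right. A reader might infer that the rule flatters the drug. That would need exclusion to mean removal from the primary analysis, which Section 4.1 does not say, and severe patients to be removed more often, for which there are no data. Section 1.1 gives no frequency for breaks over two weeks. It also connects compliance with cancer treatment to breaks; it does not show that failure to use the rinse follows mucositis severity. The 25% figure in step 4 assumes that half of severe patients and nobody else are excluded, which nothing in the documents supports. The NRPS shift of 0.27 on a 0-10 scale is small.

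**The 38% figure.** A reader might take it as the trial's chance of falling short. It treats the tolerated loss as the expected loss. Section 8.1 speaks of a minimum of 10, so 15 may include a margin, and at 80% completion the chance is 6%.

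**Conclusion.** The point holds as a conflict between stated rules and should be fixed. Replacement of compliance dropouts is both required and forbidden. Replacement of break patients has no limit in Section 4.1 and a limit of 15 elsewhere. Exclusion for a break has no defined meaning in any analysis set, and the primary efficacy set is contradictory. These findings rest on the text alone.

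The selection concern is conditional. It applies if excluded means removed from the primary efficacy analysis, and its size and direction cannot be found from the documents. It is zero if exclusion is unrelated to severity. The 30% to 50% spread in step 3 shows how far the choice of rule can move one assumed dataset; it does not estimate bias, and the intervals overlap widely.

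**What to change.** 1. State one replacement rule and one enrolment maximum in Sections 4.1, 6.6 and 8.1, for example no replacement and at most 15 enrolled. Keeping replacement is also workable if the maximum is stated and replaced patients stay in the FAS.
2. State in Section 4.1 that patients with poor compliance or a radiation break over two weeks remain in the FAS if they meet Section 8.4.2.
3. Make the FAS the single primary efficacy set, and change Sections 8.5.4 and 7.6.1 to agree.
4. Add a radiation break over two weeks to the PP violations in Section 8.4.3. Apply break and compliance exclusions only in the PP analysis, and show that result beside the FAS result.
5. Report the number and timing of such breaks and of noncompliance.

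**Cost.** These are wording changes and a short additional summary. There are no extra patients unless replacement is kept. The result may look less favourable. Patients with early breaks will be in the FAS with less radiation by Day 36, which is why the PP result must stand next to it. Without replacement, fewer than 10 may complete: a 6% to 60% chance for assumed completion rates of 80% down to 60%.

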4.2 Inclusion Criteria

Patients will be included in the trial if they meet all of the following criteria:

1. Subjects with head and neck cancer involving the oropharynx or oral cavity, who are expected to undergo high dose radiation therapy (i.e., ≥ 60 Gy) that typically results in oral mucositis, with or without concurrent chemotherapy or biologic targeted therapy.
2. At least 18 years of age
3. Estimated survival of at least 6 months.
4. No prior radiation therapy to the head and neck area, and no chemotherapy within the last year except for induction chemotherapy delivered (or to be delivered) prior to the current course of radiation therapy
5. Female subjects of child-bearing potential must agree to use an adequate form of contraceptive (e.g., hormonal, barrier method or abstinence) prior to study entry and for the duration of the trial.
6. Are willing to refrain from using other treatments for oral mucositis until they consult with the study investigator(s).
7. Are able to give written informed consent in a manner approved by the Institutional Review Board and comply with the requirements of the study.

4.3 Exclusion Criteria

Patients will be excluded from the trial if they meet any of the following criteria:

1. Have preexisting mucositis from other causes.
2. Are immunosuppressed or in chronic use of immunosuppressive drugs.
3. Have a known sensitivity to any of the constituents of the test product including sensitivities to sandalwood oil, fragrances or any member of the Compositae family of vascular plants (e.g., sunflowers, daisies, dahlias, etc.).
4. ECOG performance status ≥ 3
5. Unwilling or unable to follow the protocol requirements.
6. Have any condition that in the opinion of the investigator would confound the efficacy,

safety and tolerability assessments, such as oral thrush.

7. Have participated in any clinical trial in the previous 30 days.
8. Are pregnant, breastfeeding, or unwilling to practice an acceptable form of birth control during the study.

5.0 Patient Enrollment

The Investigator or designee will be expected to maintain a log of screened patients and an Enrollment Log of all patients enrolled in the study indicating their assigned study number.

This is an open-label study so there is no randomization. Each patient will receive active product.

As noted in Section 8.1.2, each potential patient will sign and date an informed consent form before any study specified procedures are performed.

Once a potential patient is determined to be eligible for inclusion in the study, site personnel will dispense study medication according to this protocol.

6.0 VISIT SCHEDULE AND ASSESSMENTS

6.1 Study Procedures

The visit schedule and assessments are summarized in Table 5-1. A patient will have a maximum of 10 visits: a pretreatment Visit (Visit 1), weekly treatment visits (Visit 2 – 8), and if the mucositis persists, follow-up visits (Visit 9 -10) every other week until the patient's mucositis has resolved which is estimated out to be approximately 9 to 11 weeks after Day 1 treatment initiation.

Source documents will be completed at each patient's visit, and the data captured in the source documents will be subsequently entered into the case report forms (CRFs) by the Investigator or designee.

Table 6–1 Time and Events

Footnotes to Table 1: Time and Events

- ^a Site staff will follow the requirements of the local IRB if required to obtain informed consent from the subjects.
- ^b Only pertinent medical history will be recorded for each subject including smoking history and alcohol intake.
- ^c A serum pregnancy test will be completed for all women of child-bearing potential before radiotherapy simulation.
- ^d Adverse events will be collected after the subject's first treatment and throughout the trial.

6.2 Study Visits and Contacts

6.2.1 Treatment Period: Visit 2 Baseline (Day 1 or at Validation)

The following procedures will be completed at Visit 2 (Baseline) after the informed consent process has been completed and the informed consent form signed.

- Review and update the subject's medications and PEG tube usage
- Inspect the oral cavity for any abnormalities that could potentially confound study results
- Administer the Numerical Rating Pain Scale (NRPS) as related to mouth pain and pain with swallowing. The NRPS will be recorded daily by the subjects between study visits.
- Administer the QoL Questionnaire
- Provide the subject with the products, directions for use and diaries. Be sure to weigh the study medication container(s) to ensure an accurate weight of the unused medication is obtained at Visit 1 and for future comparisons
- Review Day 1 of the diary for completeness and accuracy

6.2.2 Treatment Period: Visit 2 to 8

During the treatment period, subjects will be evaluated by the treating physician once a week. If it is not possible for the subject to come in for the scheduled study visit, the visit can be conducted 2 days earlier or later, but the study personnel should attempt to get the subject back on schedule at the next study visit.

The following procedures will be completed.

- Query for adverse events
- Update concomitant medications and PEG tube usage
- Review the diary of the previous week
- Query for treatment regimen compliance
- Collect the study medication and weigh the study medication to determine usage
- Dispense study medication, as necessary
- Administer the QoL Questionnaire
- Administer the Numerical Rating Pain Scale (NRPS) as related to mouth pain and pain with swallowing. The NRPS will be recorded daily by the subjects between study visits.
- Inspect the oral cavity and grade mucositis according to the RTOG Scale
- Record the subject's tolerability to the study drug
- Instruct the subject to return for the next study visit with study medication container and diary

6.2.3 Follow-up Period: Visit 9 to 10

Clinic visits with a radiation oncologist every other week after completion of radiotherapy until mucositis has resolved.

Study visits will have a \pm 2 day window during the follow-up period.

- Query for adverse events
- Update concomitant medications and PEG tube usage
- Review the diaries of the previous week.
- Query for treatment regimen compliance
- Collect the study medication and weigh the study medication to determine usage
- Dispense study medication, as necessary
- Administer the QoL Questionnaire
- Administer the Numerical Rating Pain Scale (NRPS) as related to mouth pain and pain with swallowing. The NRPS will be recorded daily by the subjects between study visits.
- Inspect the oral cavity and grade mucositis according to the RTOG Scale
- Record the subject's tolerability to the study drug
- Instruct the subject to return for the next study visit with study medication container and diary

6.3 Interruption or Discontinuation of Treatment

Every subject has the right to refuse further participation in the study at any time and without providing reasons (see also Section 8.1.2). A subject's participation is to be terminated immediately upon his/her request. The investigator should seek to obtain the reason and record this on the case report form (CRF).

Should the subject, during the course of the study, develop conditions which would have prevented his/her entry into the study according to the safety related medical exclusion criteria, he/she must be withdrawn immediately.

The subject may be withdrawn from the study at any time at the discretion of the investigator for medical reasons and/or due to non-adherence to the treatment scheme and other duties stipulated in the study protocol. The reasons are to be fully documented on the CRF.

In addition, the sponsor and the investigator reserve the right to end or suspend the study at any time (see Section 8.2.3).

6.4 Withdrawals

The following medical and other reasons justify a premature termination (by subject or investigator) of any of the study products:

- Adverse event (including any SAE, clinically significant AE, intercurrent illness, or other medical condition that indicates to the investigator that continued participation is not in the best interest of the subject);
- Death;
- Lost to follow-up;
- Noncompliance with study medication dosing regimen, protocol requirements, or study-related procedures;
- Investigator discretion in case of occurrence of any medication condition, requirement for prohibited concomitant medication or treatment, or circumstances that would not allow the subject to adhere to protocol requirements;
- Pregnancy;
- Study terminated by Sponsor;
- Withdrawal of consent;

If a subject withdraws from the study, all efforts will be made to complete a final evaluation, if possible. Subjects discontinued due to an AE will be followed until the AE is resolved, a reasonable explanation is provided for the event, or the subject is referred to his/her own primary medical doctor. The specific AE in question will be recorded on the appropriate CRF. All subjects who are withdrawn should complete return to the clinic for a final assessment.

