Trial Design and Subject Population	
This trial will be a single-center, open-label, proof of concept trial to evaluate the efficacy, safety and tolerability of SAN005 treatment regimen when administered to adults at least 18 years of age for the prevention and treatment of oral mucositis.
 
Subjects will enter the Screening Period once the informed consent process has been completed. Subjects who are scheduled to receive radiation with or without concurrent chemotherapy and meet all of the inclusion criteria and none of the exclusion criteria will be eligible for the study:
 
Once subject eligibility is confirmed the subject will start SAN005 treatment on Day 1 of their radiation treatment. All subjects will receive active medication in the study with the first dose administered on Day 1.
 
Subjects will be instructed on the administration of study medication thrice daily throughout the duration of radiation therapy. Subjects will be evaluated by the physician once a week while receiving radiation therapy and then every other week once their radiation therapy has been completed, until their mucositis has resolved for the Final Study Visit.

Inclusion Criteria

Subjects will be included in the trial if they meet all of the following criteria:

1. Subjects with head and neck cancer involving the oropharynx or oral cavity, who are expected to undergo high dose radiation therapy (i.e., ≥ 60 Gy) that typically results in oral mucositis, with or without concurrent chemotherapy or biologic targeted therapy.
2. At least 18 years of age
3. Estimated survival of at least 6 months.
4. No prior radiation therapy to the head and neck area, and no chemotherapy within the last year except for induction chemotherapy delivered (or to be delivered) prior to the current course of radiation therapy
5. Female subjects of child-bearing potential must agree to use an adequate form of contraceptive (e.g., hormonal, barrier method or abstinence) prior to study entry and for the duration of the trial.
6. Are willing to refrain from using other treatments for oral mucositis until they consult with the study investigator(s).
7. Are able to give written informed consent in a manner approved by the Institutional Review Board and comply with the requirements of the study.

Exclusion Criteria

Subjects will be excluded from the trial if they meet any of the following criteria:

1. Have preexisting mucositis from other causes.

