6.5 Withdrawal Procedures

Protocol-specified withdrawal procedures are the same as those to be performed at the last study visit (Section 6.2.9).

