7.3.1 Dose Modification

In the event a subject experiences any health issue in the treatment area during the study, the subject should be examined by the study physician. All AEs should be recorded in the case report forms (CRFs) and any reactions to study product must be reported to the study coordinator.

If a subject experiences an allergic reaction to the study drug oral diphenhydramine may be administered according to package labeling if necessary.

Upon resolution of any reaction (localized or generalized), the subject may be re-challenged with study treatment at the discretion of the treating physician after careful analysis of the possible cause of the reaction. The investigator or designee must stress the importance of using the study treatment according to the instructions provided. In the absence of further reactions, study treatment may resume. If a reaction recurs, treatment should be stopped. Subjects should report to the study physician, and they will be discontinued from the study.

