7.5 Treatment Compliance

Records of study product used and intervals between visits will be kept during the study.

Product accountability will be noted by the study monitor during site visits and at the completion of the trial.

Subjects will be asked to return all partially used and empty products to the study site at each visit. The products will be weighed prior to dispensation and at each study visit and the weight difference will be analyzed as a measure of product usage. Subjects who are consistently noncompliant (ie, < 80% of required doses) will be counseled and may be withdrawn from the study. Subjects will be asked to return all unused product at the end of the study.

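### Stopping SAN005 is not separated from leaving the study, so subjects who leave before Day 36 have no planned Visit 7 RTOG or NRPS value

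*Combined protocol and SAP*

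**What the plan says.** Section 3.2 places the primary efficacy assessment, NRPS and RTOG grade, at Visit 7 (Day 36). Section 3.1 says overall efficacy is judged against historical controls.

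Section 6.4 is headed as dealing with withdrawals, but its list concerns the product: "The following medical and other reasons justify a premature termination (by subject or investigator) of any of the study products". The list includes adverse events, noncompliance and investigator discretion. The next paragraph concerns the study: "If a subject withdraws from the study, all efforts will be made to complete a final evaluation, if possible". It adds that withdrawn subjects should return for a final assessment, and that those discontinued for an AE are followed for that AE. Section 6.5 equates the withdrawal procedures with those of the last study visit and cites Section 6.2.9, which does not exist.

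Other sections also lead from product to study exit:

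- Section 7.3.1, if a reaction recurs after re-challenge: "Subjects should report to the study physician, and they will be discontinued from the study".
- Section 6.3: a subject who develops a condition covered by the safety-related exclusion criteria must be withdrawn. Withdrawal for medical reasons or non-adherence is at the investigator's discretion.
- Section 7.5: subjects consistently below 80% of doses "will be counseled and may be withdrawn from the study".

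On analysis, the FAS (8.4.2) needs one dose and includes a subject "who had at least one post-Baseline efficacy assessment". The PP set (8.4.3) drops anyone below 80% compliance or without a Week 5 observation. Section 8.4.2 calls the FAS primary and Section 8.5.4 calls the PP set primary. Section 7.6.1 limits the efficacy analysis to subjects with at least 80% of treatments.

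**The concern.** The plan has no status for a subject who is off product but still on study. Someone who stops the rinse and is withdrawn before Day 36 gives the values collected up to that point and one final assessment, and then no further efficacy data.

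The reasons for stopping are unlikely to be independent of the outcome. The rinse is taken into an irradiated mouth, Section 7.7 and Appendix 1 expect some burning or irritation, and the endpoints are mouth pain and mucosal injury. If those who stop tend to have worse mouths at Day 36, the Visit 7 summary and the historical-control comparison are too favourable. Time to onset, duration and PEG use, all named in Section 3.1, are cut short for the same subjects.

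The loss cannot be repaired at analysis, because neither analysis set can supply a value that was never collected and the documents give no rule for a missing Visit 7 value.

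**Working it through.** **Step 1. Follow a subject who exits before Day 36.**

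- Efficacy data after exit: one final assessment. If it follows last-visit procedures it records RTOG grade and NRPS, but on an unspecified date. It serves as Visit 7 only if it happens to fall within 2 days of Day 36.
- Safety data after exit: AE follow-up (6.4), and SAE and death reporting until 4 weeks after stopping (7.8.1.3). Neither includes scheduled RTOG or NRPS.
- FAS: the subject is kept if there is one post-baseline assessment, with no Visit 7 value.
- PP: the subject is dropped for lacking the Week 5 observation, and possibly for compliance as well.

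Choosing either set as primary leaves the Day 36 value missing.

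**Step 2. Could the data be collected?** The synopsis says: "Subjects will be evaluated by the physician once a week while receiving radiation therapy". Section 6.2.2 says the same of the treatment period. Nothing ties stopping the rinse to stopping radiotherapy. Continued weekly contact up to Day 36 is therefore a reasonable inference, though the documents do not state it for withdrawn subjects.

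**Step 3. The plan's own figure.** Section 8.1: "Up to 15 subjects will be enrolled in this study to ensure a minimum of 10 subjects complete the study". Non-completion allowed: 15 − 10 = 5, and 5/15 = 33.3%. Equivalently 10/(1 − 1/3) = 15, but the one-third is taken from 15 and 10, so this is not an independent check. No dropout rate, alpha, power or effect size is given, and Section 8.2 says the study is not powered.

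**Step 4. Upper limit on what is unknown.** Let k of 15 subjects lack a Visit 7 value.

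- Binary outcome: with x events observed, the proportion among the 15 lies between x/15 and (x + k)/15. Width = k/15.
- Mean NRPS (0 to 10, Appendix 1): each missing score can be anything from 0 to 10. Width = 10k/15. With baseline scores known, the mean change from baseline has the same width.

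| k missing | Binary outcome, width (percentage points) | Mean NRPS, width (points) |
|---|---|---|
| 1 | 6.7 | 0.67 |
| 2 | 13.3 | 1.33 |
| 3 | 20.0 | 2.00 |
| 4 | 26.7 | 2.67 |
| 5 | 33.3 | 3.33 |

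**Step 5. Illustration with assumed data and k = 5.** If 4 of 10 observed subjects have grade 3 or higher, the reported rate is 4/10 = 40%. The rate among all 15 lies between 4/15 = 27% and 9/15 = 60%. If the 10 observed subjects average NRPS 4, the mean among all 15 lies between (40 + 0)/15 = 2.7 and (40 + 50)/15 = 6.0. The counts and means are assumptions; only 15 and 10 come from the plan.

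**The case against.** A reader might infer that every subject who stops SAN005 is automatically withdrawn. The text does not say so. The reasons in Section 6.4 justify ending product, and its sentence on withdrawal is conditional. Section 7.5 and part of Section 6.3 say that a subject may be withdrawn. Section 7.3.1 allows re-challenge after a first reaction. Only a recurrent reaction and a newly arising safety-related exclusion condition require exit. A reader might also infer that nothing but one evaluation is collected afterwards, but AE and SAE follow-up continues, and the RTOG and NRPS values recorded before exit are kept.

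The allowance of 5 in 15 covers more than early product stoppers. It also takes in radiation breaks of more than two weeks (4.1), death, loss to follow-up, withdrawn consent and exits after Visit 7. Some of these cannot be recovered and some already have a Visit 7 value.

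Further, most early stoppers would leave a PP-based primary analysis through the 80% rule even with a complete record, so collecting the data changes nothing unless the analysis rules are aligned. This objection stands, and the remedy has to meet it.

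Finally, this is a small, descriptive, unpowered proof-of-concept trial, where an on-treatment focus is defensible. The body of Table 6-1 is also missing from the text reviewed, so an early-termination column cannot be ruled out. Such a column would help only if it kept assessments going to Day 36. An on-treatment summary can still be reported when off-product data exist, whereas an all-treated summary cannot be built without them.

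**Conclusion.** The gap is real. Two routes require study exit, others permit it, and no section provides for RTOG or NRPS at Day 36 in a subject who has left. Each missing subject adds 6.7 percentage points of uncertainty to a binary outcome and 0.67 points to mean NRPS across 15 subjects. The ceiling is 33 percentage points and 3.3 NRPS points, if all five allowed non-completers lack Visit 7 data. The part due to this gap is smaller, for the reasons given above, and cannot be estimated from the documents.

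A reader might go on to infer that the result will be biased in favour of SAN005 by a definite amount. The documents do not support that. The direction is plausible because stopping a rinse is likely to track mouth symptoms, but a reaction to the product need not track mucositis severity, and no stopping rate or outcome among stoppers is given.

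The sizes assume 15 enrolled. Sections 4.1 and 6.6 disagree on whether dropouts are replaced, so the number could be larger.

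**What to change.** Leave the rules on when product is stopped as they are. In Sections 6.3, 6.4, 7.3.1 and 7.5, distinguish stopping SAN005 from leaving the study. State that a subject who stops SAN005 remains on study for data collection unless consent is withdrawn, the subject dies or is lost to follow-up, or the sponsor ends the study. The sentences in 6.3 and 7.3.1 that now require study exit need rewording to match.

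For these subjects, record RTOG grade, NRPS, PEG use, concomitant medication and AEs on the existing schedule through at least Visit 7, and at follow-up visits where the subject attends. Put the date and reason for stopping on the CRF.

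So that the values reach the efficacy summary:

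- include them in the FAS summary at Visit 7;
- state that the 80% restriction in Section 7.6.1 applies to the PP set only, and word the exclusion of poor-compliance dropouts in Section 4.1 to agree;
- reconcile Sections 8.4.2 and 8.5.4 on which set is primary.

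Correct the reference in Section 6.5 to the non-existent Section 6.2.9.

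The cost is protocol wording and a CRF field. Up to Day 36 the assessments can use the weekly radiotherapy visits, if attendance continues as expected. Some subjects who stop may not keep the daily diary, so NRPS at the visit is the minimum to aim for. The summary will include off-product assessments and may look slightly less favourable; the PP summary can still be shown beside it.
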